6.5. Missing Data

Every effort will be made to minimize missing data and collect all outcome measures specified in this protocol. Participants who discontinue treatment will be followed after treatment discontinuation for collection of all scheduled follow-up data with their consent.

Missing dose data (dosing time, or dosing date) will be imputed to maximize the inclusion of observations subsequent to doses with missing information. Missing dosing time will be imputed if the dose date and amount are available:

- If dosing times are missing, the pre-dose sample time combined with the dose number and dosing timeline will be used to determine the pre-study and on-study dosing times.
- Dosing time will be imputed as the mean of the time from pre-dose draw to dosing for those not missing the given sampling window.

Missing covariate data for analyses that incorporate confounding covariate variables will be handled in the following manner. The covariate will be excluded from the analysis if more than 20% of the covariate values are missing. Baseline individual covariates, including sex and weight group, will be determined from the Day 1 visit. If an individual's baseline covariate is missing at the Day 1 visit, the baseline covariate value will be taken from either the pre-study (screening) visit or from the earliest post-dose visit, whichever is closest to the baseline visit. Receipt of IV artesunate or artemisinin-based therapy before enrollment will be determined from treatment administration records with dates and times before the first on-study dose and/or concomitant medication records with dates up to the Day 1 visit. Receipt of oral ACT, which has planned collection occurring after baseline, will be determined from all visits up to and including the visit at which the analysis timepoint occurs.

No imputation will be performed for missing primary or secondary PD outcome response variables. Rather, only participants in the PD Analysis Population with the PD outcome response variable measured at the timepoint of interest will be included in PD analyses of that PD outcome response variable measured at the timepoint of interest.

Please refer to the Pharmacometrics Analysis Plan for details pertaining to methods for missing concentration data and other missing data that would affect the PK analysis.

6.6. Interim Analyses and Data Monitoring

An Independent Safety Monitor (ISM) will be utilized for study. The ISM is a physician with relevant expertise whose primary responsibility is to provide to DMID an independent safety assessment in a timely fashion. Participation is for the duration of the DMID study and is a voluntary position that does not receive payment.

The ISM is near the study site and has the authority and ability to readily access study participant records in real time. The ISM may be a member of the participating institution's staff but preferably be from a different organizational group within the institution. The ISM should not be in a direct supervisory relationship with the investigator and have no direct involvement in the conduct of the study.

The ISM will receive reports of SAEs from the site investigator and will be notified by email when the Infectious Diseases Institute (IDI) Research Ethics Committee (REC) and DMID are notified of the SAE. The ISM will then evaluate the SAE and report their clinical assessment to the REC and DMID, through DMID-Clinical Research Operations and Management Support (CROMS) Safety Oversight Committee Support (SOCS) and via email. The ISM will also communicate with the investigator at the participating site as needed, review additional safety related events at the request of the REC and DMID, and provide additional information to REC and DMID by teleconference as requested.

Results of the primary and secondary data analyses will be included in an interim CSR once the primary study outcome measure is reached at Day 183 (± 14). No other formal interim analyses are planned for this study.

6.7. Multicenter Studies

This is a single-site study.

6.8. Multiple Comparisons/Multiplicity

The primary analysis involves assessing multiple exposure-response relationships measured at multiple timepoints, which can be framed as a series of hypothesis tests to evaluate these potential relationships. To accommodate the multiple hypothesis tests in the primary analysis, the set of p-values corresponding to tests of the effect of exposure on response at each timepoint will be adjusted using the Benjamini-Hochberg procedure to preserve the false discovery rate for the primary outcome at 0.05. There are no adjustments for multiple comparisons planned for secondary or exploratory analyses.

7. STUDY PARTICIPANTS

7.1. Disposition of Participants

[Table 9](#) will present a summary of the reasons participants were screened but not enrolled. Enrolled participants who were ineligible for inclusion in analysis populations will be summarized by reason for participant exclusion in [Table 7](#). A listing of participants that received investigational product will be provided in [Listing 1](#). Individual listings of participants who were excluded from the Safety Population, the Population PK Analysis Population, or the PD Analysis Population will be listed ([Listing 5](#)).

The disposition of participants in the study will be tabulated in [Table 5](#). The table shows the total number of participants screened, enrolled, receiving IV artesunate or other artemisinin-based therapy before enrollment, receiving IV artesunate before enrollment, receiving on-study IV artesunate, receiving oral artemisinin-combination therapy, discharged from the hospital, having at least one measurable DHA concentration, having at least one estimable PK exposure parameter, having post-baseline PD response data collected, completing all blood draws, and completing the study. A flowchart showing the disposition of study participants will be included ([Figure 1](#)). This figure will present the number of participants screened, enrolled, lost to follow-up, and analyzed. Additionally, the number of participants with reported assessed signs and symptoms contributing to the definition of severe malaria at enrollment will be presented in [Table 6](#). A summary of dosing of IV artesunate and on-study oral ACT is presented in [Table 8](#). A listing of participants who discontinued treatment or terminated early from study follow-up with the reason for discontinuation or termination will be included in [Listing 2](#). Listings of the actual dosages of IV artesunate and on-study oral ACT administered for each participant are provided in [Listing 8](#) and [Listing 9](#), respectively.

7.2. Protocol Deviations

A summary of participant-specific protocol deviations will be presented by deviation category and deviation type for all enrolled participants in [Table 4](#). Deviations will be reviewed by the Sponsor for possible participant exclusion from the per protocol population and will be classified as either major or minor. This table will provide both the number of participants and the number of deviations for each deviation category and deviation type. All participant-specific protocol deviations and non-participant-specific protocol deviations will be listed in [Listing 3](#) and [Listing 4](#), respectively.

8. PHARMACODYNAMICS EVALUATION

All model-based primary and secondary PD analyses will adjust for a subset of the following covariates: sex, weight group (<20 kg or \geq 20 kg), receipt of IV artesunate or artemisinin-based therapy before enrollment, and receipt of concomitant medications. Where appropriate, primary and secondary PD analyses may also adjust for receipt of oral ACT. Exploratory boxplots and stacked bar graphs of response variables by covariate values, and by timepoint when appropriate, will inform covariate selection for each model.

Primary and secondary analyses will be performed using the Pharmacodynamics Analysis Population, and a sensitivity analysis will be performed for each primary and secondary analysis including only participants who did not receive IV artesunate or other artemisinin-based therapy before enrollment.

8.1. Primary Pharmacodynamics Analysis

The primary PD analysis will be performed to assess the relationship between DHA PK exposure parameters, including AUC_{0-12} , C_{max} , $t_{1/2}$, and T_{max} , and markers of physiological dysfunction known to be associated with severe malaria. These markers of physiological dysfunction measured at planned follow-up times will be the primary outcome response variables, and will include temperature, systolic and diastolic blood pressure, serum lactate, serum bicarbonate, serum glucose, BCS, total and direct bilirubin, hemoglobin, and creatinine. Values of AUC_{0-12} , C_{max} , $t_{1/2}$, and T_{max} for each participant will be treated as fixed in all PD analyses. Details of the calculation of AUC_{0-12} , C_{max} , T_{max} , and $t_{1/2}$ can be found in the Pharmacometrics Analysis Plan.

Planned follow-up times at which the relationships between each marker of physiological dysfunction and exposure parameter will be assessed include:

- Approximately 24 hours post-first dose, for which the most recent measurement of each physiological dysfunction variable before 24 hours post-first dose will be utilized as the response;
- Approximately 48 hours post-first dose, for which the most recent measurement of each physiological dysfunction variable before 48 hours post-first dose will be utilized as the response;
- Time of completion of the final planned dose of IV artesunate, for which the first measurement of each physiological dysfunction variable after completion of the final planned dose of IV artesunate will be utilized as the response; and
- Time of first hospital discharge, for which the most recent measurement of each physiological dysfunction variable before the time of first hospital discharge will be used as the response.

Exploratory scatterplots of each continuous primary outcome response variable will be presented by exposure parameter and timepoint beginning in [Figure 2](#) and continuing through [Figure 11](#) for the PD Analysis Population. Exploratory box plots of BCS will be presented by exposure parameter and timepoint in [Figure 12](#). Summary statistics for each continuous marker of physiological dysfunction and its change from baseline will also be presented by parameter and timepoint in [Table 13](#) for participants in the PD Analysis Population and in [Table 14](#) for the subset of the PD Analysis Population with no IV artesunate or other artemisinin-based therapy before enrollment. Proportions of participants with each BCS value will be presented by timepoint in [Table 15](#) for participants in the PD Analysis Population and in [Table 16](#) for the subset of the PD Analysis Population with no IV artesunate or other artemisinin-based therapy before enrollment.

Regression models will be fit to characterize the relationship between each primary outcome response and each exposure parameter at each of the above timepoints, controlling for covariates (given in Section 6.4). Note that receipt of oral ACT will only be considered for inclusion in analyses of the primary outcome

response variables at time of first hospital discharge. Exploratory boxplots of each continuous primary outcome response variable will be presented by covariate and timepoint beginning in [Figure 13](#) and continuing through [Figure 22](#). Exploratory stacked bar charts of BCS will be presented by covariate and timepoint in [Figure 23](#). These exploratory plots, presented for the PD Analysis Population, will be used to inform what subset of covariates will be included in each model.

Proportional odds mixed effects models will be used to assess the relationship between each exposure parameter and ordinal BCS at each timepoint. The proportional odds mixed effect model for BCS at any one of the four timepoints considered is defined as follows:

$$\text{logit}\{\tau_k(P_i, t_i, BCS_{0,i}, X_i)\} = \alpha_k + \beta_1 P_i + \beta_2 t_i + \eta^T X_i + BCS_{0,i} + b_i.$$

In the above model, $\tau_k(P_i, t_i, BCS_{0,i}, X_i) = \Pr(BCS \leq k | P_i, t_i, BCS_{0,i}, X_i)$ represents the cumulative probability that BCS will be less than or equal to $k \in \{0,1,2,3,4,5\}$ given the covariates. The BCS level-specific intercept is represented by α_k , P_i is the exposure parameter value for the i th participant, t_i is the actual response measurement time post-first dose, $BCS_{0,i}$ is the baseline BCS for the i th participant, and X_i are the values for the i th participant of the additional covariates included in the model. The β_1 , β_2 , and η are model parameters associated with the above covariates. The term b_i represents a participant-specific random intercept, where it is assumed that b_i follow a normal distribution with mean zero and nonzero variance. For 24 hours and 48 hours post-first dose timepoints, t_i will be measured in hours post-first dose rounded to the nearest tenths place. For time of completion of the final planned dose of IV artesunate and time of first hospital discharge timepoints, t_i will be measured in days post-first dose rounded to the nearest tenths place.

The following pseudocode will be used to fit the proportional odds mixed effects models for BCS and to extract the p-value for the exposure model parameter.

```
/* Proportional odds model fit and output p-values */
proc glimmix data=dataset(where=(population=p and response=r));
*catvar = any categorical covariates included in the model;
*refvalues = the value(s) to be used as the reference level for categorical
covariate(s);
class catvar(ref=refvalues);
*baseresp = response at baseline;
*othercovars = any other covariates (including those specified in the class statement)
included in the model;
model resp = baseresp exposure time othercovars / dist=multinomial link=cumlogit;
random intercept;
by timepoint;
ods output Tests3=tests3;
run;
data tests3; set tests3(where=(effect='EXPOSURE')) ;
rename ProbF=pval;
run;
```

For the continuous primary outcome response variables, if model assumptions hold, Emax models will be fit for each primary outcome effect and each exposure parameter at each timepoint. The Emax model for primary outcome effect, E_i , is defined as follows:

$$E_i = E_{0,i} + \frac{E_{max} \times P_i^\gamma}{EC_{50}^\gamma + P_i^\gamma} + e_i,$$

where E_i represents the given response outcome measure for the i th participant at the given timepoint, $E_{0,i}$ is the baseline response outcome effect for participant i , E_{max} is the maximum effect, EC_{50} is the exposure at half-maximal effect, P_i is the exposure parameter value for participant i , γ is the Hill parameter [7, 8] or slope coefficient, and e_i are the measurement errors for participant i . These measurement errors are assumed to be independent and normally distributed with mean zero and nonzero variance. E_{max} , EC_{50} , and $E_{0,i}$ may be modeled with fixed covariate effects, i.e., $E_{max} \sim X_i$ where X_i are the subset of covariates included for E_{max} . The subset of covariates included may differ between E_{max} , EC_{50} , and $E_{0,i}$. Alternatively, E_{max} , EC_{50} , and $E_{0,i}$ may be considered random effects if fixed effects are not included. For example, $E_{0,i}$ may also be modeled instead with a random effect, whereby an additive random component with mean-zero normal distribution will be assumed for $E_{0,i}$ such that $E_{0,i} = E_0 + b_{1i}$, where E_0 , is the population-level quantity and b_{1i} are independently normally distributed random effects with mean zero and nonzero variance. Model selection will proceed in a forward direction from least complex model (no fixed covariates included on any of the above parameters) to more complex. Estimated log-likelihood statistics or other convergence criteria will be used to assist in Emax model selection.

If Emax models are fit for a primary outcome effect, the following pseudocode will be used for model fitting and to extract p-values for the exposure model parameter

```

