7 STUDY SCHEDULE

7.1 Screening

Starting at the emergency department of the hospital, participants diagnosed by the attending physician and have received a prescription of artesunate for severe malaria will be screened for study eligibility and enrolled.

Recruitment will be progressive over a single malaria transmission season so that up to 100 children of either sex who fulfill the inclusion criteria are enrolled. Participants will be recruited by non-coercive methods among children aged 6 months-14 years residing near the study site. A parent/guardian of a child diagnosed with severe malaria will be informed of the study to determine if they are interested to have their child participate. Children who are of the age of assent (age 8 in Uganda) and above and who are conscious will also be informed of the study to determine if they are interested. Informed consent of a parent/guardian and assent for children ≥ 8 and <18 years of age who are conscious at enrollment and otherwise able to provide assent is required for enrollment. After the study has been explained to a potential participant's parent/guardian, and to a potential participant in the case of a conscious child aged 8-14 years old, they will be provided with a copy of the consent form and assent form if applicable. The consent/assent process will be conducted in a semi-private area to ensure confidentiality, to reduce the likelihood of other participants influencing their decision, and to allow further time to make a final decision. A single informed consent document, and a single assent document when applicable, will be used for screening and other study procedures. Only participants who receive a first dose of IV artesunate are considered enrolled in the study. Administration of artesunate therapy will not be delayed for enrollment procedures. Participants may still be enrolled up to 24 hours after first dose of IV artesunate. In the case of unconscious children who are the age of assent, only informed consent of a parent/guardian is required for enrollment. Once the child becomes conscious, assent will be obtained from the child to determine if their participation in the study will continue.

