8 STUDY PROCEDURES/EVALUATIONS

8.1 Daily Study Procedures

Screening (may take place over more than one visit) up to 24 hours before enrollment

- Written assent for children \geq 8 years as applicable
- Informed consent obtained from the parent
- Check of inclusion and exclusion criteria
- Participant identification number assigned
- Demographics and medical history of participant
- Concomitant medication documentation
- Physical examination and vital signs (pulse, respiratory rate, blood pressure, axillary temperature)
- Document height and weight
- BCS
- Urinalysis
- Collect 8.25 mL venous blood sample for:
 - Hematology: hemoglobin, platelets, WBC count, neutrophil count
 - Biochemistry: serum creatinine, AST, ALT, total and direct bilirubin, bicarbonate, lactate, sodium, potassium, glucose, BUN, calcium
 - *P. falciparum* parasite quantification
 - Artemisinin resistance
 - Population PK study per sampling plan specified in Section 8.3.1
 - *P. falciparum* mRNA collection using PAXgene tube

Day 1 Enrollment

- Physical examination and vital signs (pulse, respiratory rate, blood pressure, axillary temperature every 6 hours until 6 hours post-parasite clearance)
- Urinalysis

- An IV cannula will be inserted for administration of study drugs and for PK blood sampling and blood draws.
 - Collect venous blood samples for population PK study per sampling plan specified in Section 8.3.1
 - Administration of IV artesunate dose in accordance with WHO and Uganda guidelines
- Collect 11.5 mL venous blood sample for:
 - Hematology: hemoglobin, platelets, WBC count, neutrophil count (at least 12 hours after initial screening collection)
 - Biochemistry: serum creatinine, AST, ALT, total and direct bilirubin, serum bicarbonate, lactate, sodium, potassium, glucose, BUN, calcium (at least 12 hours after initial screening collection)
 - Population PK study per sampling plan specified in Section 8.3.1
 - *P. falciparum* parasite quantification
- Concomitant medication review
- BCS

Day 2 Follow-up

- Physical examination and vital signs (pulse, respiratory rate, blood pressure, axillary temperature)
- Administration of IV artesunate dose or ACT in accordance with WHO and Uganda guidelines
- Urinalysis
- Collect 3.5 mL venous blood sample for:
 - Hematology: hemoglobin, platelets, WBC count, neutrophil count
 - Biochemistry: serum creatinine, AST, ALT, total and direct bilirubin, serum bicarbonate, lactate, sodium, potassium, glucose, BUN, calcium

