3.3. Study Definitions and Derived Variables

Severe Malaria

Severe malaria is defined as presence or history of fever plus a positive blood film for *P. falciparum* malaria with at least one of the following symptoms and signs:

- Repeated convulsions: More than two episodes within 24 h
- Impaired consciousness: A Blantyre coma score < 3 in children
- Coma
- Hyperpyrexia: Axillary temperature $\geq 40^{\circ}\text{C}$
- Respiratory distress: Acidotic breathing
- Inability to tolerate oral therapy and vomiting all oral intake
- Circulatory collapse or shock: Systolic blood pressure < 50 mmHg in children
- Spontaneous bleeding
- Hemoglobinuria: Hemoglobinuria presents as tea colored urine
- Jaundice
- Prostration: Extreme weakness so that the person is unable to sit, stand or walk without assistance
- Severe normocytic anaemia: Hemoglobin concentration < 5 g/dL
- Hypoglycemia: Blood or plasma glucose < 2.2 mmol/L (< 40 mg/dL)
- Renal impairment: Plasma or serum creatinine > 265 $\mu\text{mol/L}$
- Hyperparasitemia: *P. falciparum* parasitemia > 10%

Whether participants meet this definition of severe malaria will be evaluated in the process of determining enrollment eligibility. Participant history of fever, indication of positive blood film for *P. falciparum* malaria, and the presence of additional assessed symptoms and signs of severe malaria will be documented in the appropriate electronic case report form (eCRF). Only one additional sign or symptom of severe malaria must be present along with history of fever and positive blood film for *P. falciparum* malaria for a participant to meet the definition of severe malaria. Once a participant meets the definition of severe malaria, investigators may opt not to assess the participant for additional signs and symptoms. Reported symptoms and signs of severe malaria at enrollment will be summarized in [Table 6](#).

Baseline

Baseline values of primary outcome measures of physiological dysfunction, laboratory parameters, and vital signs will be defined as the most recent measurement before first dose of IV artesunate. If these measurements are not collected before first dose, such as for participants who received IV artesunate before enrollment, baseline values will be defined as either the screening measurement or the earliest measurement after first dose of IV artesunate, whichever is closest to time of first dose of IV artesunate.

Weight-for-Age and Height-for-Age Z-Scores

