Weight-for-age and height-for-age Z-scores at screening will be calculated for participants younger than 60 months using the R package “anthro” [1] which calculates Z-scores based on the WHO Child Growth Standards [2].

Pharmacokinetic Exposure Parameters

PK exposure parameters that will be used in the primary pharmacodynamics analysis include the following.

- **C_{max}** : C_{max} is defined as the maximum DHA concentration observed in plasma after the first on-study dose of IV artesunate over all PK sample concentrations.
- **AUC_{0-12}** : AUC_{0-12} is defined as the area under the concentration-time curve from first on-study dosing of IV artesunate (time 0 hours) to 12 hours post-first on-study dose of IV artesunate.
- **$t_{1/2}$** : $t_{1/2}$ is defined as the time post-first on-study dose of IV artesunate required for the DHA concentration to decrease by a factor of one half in the terminal phase.
- **T_{max}** : Time of maximum concentration (T_{max}) is defined as the time at which the C_{max} occurs.

Details of how these exposure parameters are calculated are provided in a separate Pharmacometrics Analysis Plan.

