4. INVESTIGATIONAL PLAN

4.1. Overall Study Design and Plan

This is a phase 4, single-site, open-label PK and PD study of IV artesunate in Ugandan children 6 months-14 years of age diagnosed with severe malaria according to standardized WHO criteria (any *P. falciparum* parasitemia and the presence of danger signs). Up to 100 participants from the Tororo District will be enrolled and administered standard of care IV artesunate for initial treatment of malaria with doses assigned according to WHO guidelines based on child weight [3]. Children weighing <20 kg will receive 3.0 mg/kg/dose and children weighing ≥ 20 kg will receive 2.4 mg/kg/dose for at least 24 hours. After this initial 24 hours, patients will be evaluated clinically and assessed for ability for oral intake of antimalarials. If unable to take oral medication, IV artesunate will continue at 48 and 72 hours. Children able to transition to oral antimalarial therapy after a minimum of 24 hours or later will initiate a 3-day course of oral ACT per national guidelines.

Participants will be screened up to 24 hours before enrollment and may be enrolled up to 24 hours after their first dose of IV artesunate. Participants will be enrolled and receive their first on-study dose of IV artesunate on study Day 1. All dosing times will be relative to first dose, whether this first dose occurs before enrollment or is administered on-study. The follow-up period, which will include additional dosing of IV artesunate and/or oral ACT according to WHO and national guidelines, will be approximately six months with scheduled visits on Day 2, Day 3, Day 4, Day 5, Day 6, Day 7 (± 2), Day 14 (± 2), Day 28 (± 4), and Day 183 (± 14). If a participant is discharged before study Day 7, the required follow-up visits will be on Day 7 (± 2), Day 14 (± 2), Day 28 (± 4), and Day 183 (± 14). Safety data will be monitored throughout the study by the independent safety monitor (ISM).

The overall study design is presented in [Table 1](#) and the schematic of the study design is presented in [Figure 1](#).

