14.2.2 Pharmacokinetic Response Figures by Measure and Timepoint

Figure 2: Scatterplots of Markers of Physiological Dysfunction by Exposure Parameter and Timepoint – PD Analysis Population, Temperature

[Implementation Note: This is a sample figure. This figure will have panels for every exposure parameter (AUC_{0-12} , C_{max} , T_{max} , and $t_{1/2}$) and timepoint combination. The y-axis label will be “Temperature ($^{\circ}C$)”.

Points will be color-coded based on receipt of IV artesunate or other artemisinin-based therapy before enrollment. The legend will be updated to have the title “Received IV Artesunate or Other Artemisinin-Based Therapy Before Enrollment?” and the categories “Yes” or “No”.]

Notes: Base = Baseline. 24 h and 48 h are measured from time of first dose of IV artesunate. EPD = End of Planned IV artesunate Dosing. THD = Time of first Hospital Discharge.

AUC_{0-12} is measured in $ng \cdot h / mL$, C_{max} is measured in ng / mL , T_{max} is measured in hours, and $t_{1/2}$ is measured in hours.

Figures with similar format:

Figure 3: Scatterplots of Markers of Physiological Dysfunction by Exposure Parameter and Timepoint – PD Analysis Population, Systolic Blood Pressure

Figure 4: Scatterplots of Markers of Physiological Dysfunction by Exposure Parameter and Timepoint – PD Analysis Population, Diastolic Blood Pressure

Figure 5: Scatterplots of Markers of Physiological Dysfunction by Exposure Parameter and Timepoint – PD Analysis Population, Serum Lactate

Figure 6: Scatterplots of Markers of Physiological Dysfunction by Exposure Parameter and Timepoint – PD Analysis Population, Serum Bicarbonate

Figure 7: Scatterplots of Markers of Physiological Dysfunction by Exposure Parameter and Timepoint – PD Analysis Population, Serum Glucose

Figure 8: Scatterplots of Markers of Physiological Dysfunction by Exposure Parameter and Timepoint – PD Analysis Population, Total Bilirubin

[figure not shown]
Figure 9: Scatterplots of Markers of Physiological Dysfunction by Exposure Parameter and Timepoint – PD Analysis Population, Direct Bilirubin

Figure 10: Scatterplots of Markers of Physiological Dysfunction by Exposure Parameter and Timepoint – PD Analysis Population, Hemoglobin

Figure 11: Scatterplots of Markers of Physiological Dysfunction by Exposure Parameter and Timepoint – PD Analysis Population, Creatinine

Figure 12: Boxplots of Markers of Physiological Dysfunction by Exposure Parameter and Timepoint – PD Analysis Population, BCS

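### The 24-hour response is timed from the first dose but exposure from the first on-study dose, so some primary responses precede the exposure they are regressed on

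*SAP*

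**What the plan says.** **Response clock.** For the 24-hour timepoint of the primary analysis, SAP Section 8.1 states that "the most recent measurement of each physiological dysfunction variable before 24 hours post-first dose will be utilized as the response"; the 48-hour rule has the same form. SAP Section 4.1 settles what first dose means: "All dosing times will be relative to first dose, whether this first dose occurs before enrollment or is administered on-study". The Blantyre Coma Score model uses this clock (for the 24-hour and 48-hour timepoints its time term "will be measured in hours post-first dose rounded to the nearest tenths place"), and so do the notes to Figure 2 ("24 h and 48 h are measured from time of first dose of IV artesunate").

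**Exposure clock.** SAP Section 3.3 defines AUC0-12 as the "area under the concentration-time curve from first on-study dosing of IV artesunate (time 0 hours) to 12 hours post-first on-study dose". Cmax is taken after the first on-study dose, and Tmax is the time of that Cmax. The SAP keeps the two origins apart elsewhere: Tables 23 and 24 are timed from the first on-study dose, Table 17 from the first dose.

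**How far apart they can be.** Protocol Section 7.1: "Participants may still be enrolled up to 24 hours after first dose of IV artesunate". SAP Section 4.4.5 puts the initial doses at 0, 12 and 24 hours from the first dose. SAP Table 8 has pre-enrolment rows for all three.

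**Baseline.** When no value precedes the first dose, SAP Section 3.3 says "baseline values will be defined as either the screening measurement or the earliest measurement after first dose of IV artesunate", whichever is closer to that dose. Protocol Section 8.1 schedules Day 1 hematology and biochemistry "at least 12 hours after initial screening collection", and Protocol Section 7.1 lets results from the 24 hours before enrolment serve as both screening and baseline.

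**The concern.** Section 8.1 presents the primary p-values as tests of an effect of exposure on response, so exposure has to come first. Nothing in the SAP requires this. The 24-hour rule sets an upper time limit but no lower one, and Section 6.3.3 asks for post-baseline data only for entry to the PD Analysis Population.

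Two faults follow. In pre-treated children the response may be drawn before the on-study dose, so the measured exposure is at best a proxy for exposure after earlier doses. In any child, the last laboratory value before hour 24 may be the baseline record; change from baseline is then zero whatever the exposure, which pulls the slope towards zero.

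**Working it through.** **Time order.** Let the first on-study dose fall *s* hours after the first dose. A response before hour 24 then falls less than 24 − *s* hours after the on-study dose, and the AUC0-12 window closes at hour *s* + 12.

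| *s* | Latest response relative to on-study dose | AUC window closes | Consequence at 24 h |
|---|---|---|---|
| 0 | up to 24 h after | hour 12 | order can be correct |
| 12 | less than 12 h after | hour 24 | may precede the dose; never follows the full window |
| 24 | before it | hour 36 | always precedes the dose |

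At 48 hours the order fails only if all three initial doses preceded enrolment (a boundary case under the 24-hour limit), or if the last value before hour 48 was drawn before the on-study dose.

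**Baseline as response.** Suppose the screening blood is drawn *u* hours after the first dose. The Day 1 draw comes at hour *u* + 12 or later, so with *u* > 12 it falls after hour 24. Unless the Day 2 draw comes before hour 24, the screening value is the 24-hour response and, if no earlier value exists, also the baseline. A child without prior therapy reaches the same point when no draw falls between the on-study dose and hour 24. The implementation note to SAP Table 33 allows for no child having post-baseline chemistry on Day 1.

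**Tests involved.** 11 markers × 4 exposures × 4 timepoints = 176. At 24 h: 11 × 4 = 44, mainly the 11 × 3 = 33 for AUC0-12, Cmax and Tmax. The 7 laboratory markers (lactate, bicarbonate, glucose, total and direct bilirubin, hemoglobin, creatinine) give 7 × 4 = 28 of the 44.

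**The plan's own power.** Inputs from SAP Section 5 and Table 3: 176 tests, R² = 0.2, 5% non-null (176 × 0.05 = 8.8, so 9), Benjamini-Hochberg at 0.05. With independent two-sided tests, simulation gives 0.883 at N = 80 and 0.852 at N = 75, against 0.88 and 0.85 in Table 3.

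**Misordered responses.** Let *f* be the affected share (assumed; the documents give none) and λ the fraction of the association those children keep. For the 24-hour tests R² = 0.2 × (1 − *f*(1 − λ))²; at *f* = 0.2 and λ = 0 this is 0.2 × 0.8² = 0.128. Of the 9 non-null tests, 2 are placed at 24 h (9 × 44/176 = 2.25). Power for those tests at N = 80, from 40,000 runs:

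| Handling | *f* = 2% | 5% | 10% | 20% | 30% |
|---|---|---|---|---|---|
| Kept, λ = 0 | 0.86 | 0.82 | 0.76 | 0.59 | 0.42 |
| Kept, λ = 0.5 | 0.87 | 0.86 | 0.83 | 0.76 | 0.68 |
| Kept, λ = 0.8 | 0.88 | 0.88 | 0.86 | 0.84 | 0.81 |
| Set to missing (n = 78/76/72/64/56) | 0.87 | 0.86 | 0.83 | 0.77 | 0.68 |

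At *f* = 5% and λ = 0, average power over all nine non-null tests is (2 × 0.824 + 7 × 0.883)/9 = 0.87.

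**Response equal to baseline.** Let a share *g* have response equal to baseline, and let *d* be the mean change in SD units (both assumed). Then R² = 0.2(1 − *g*)/(1 + *g d*²).

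| | *g* = 10% | 20% | 30% |
|---|---|---|---|
| R², *d* = 0 | 0.180 | 0.160 | 0.140 |
| R², *d* = 1 | 0.164 | 0.133 | 0.108 |
| Slope as a fraction of its true value | 0.90 | 0.80 | 0.70 |
| 24-h power, kept, *d* = 0 | 0.83 | 0.75 | 0.66 |
| 24-h power, kept, *d* = 1 | 0.77 | 0.62 | 0.48 |
| 24-h power, set to missing | 0.83 | 0.77 | 0.68 |

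The slopes come from a direct data simulation (N = 80, 20,000 runs, response regressed on baseline and exposure). Excluding these records restored the slope ratio to 1.00.

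**The case against.** The SAP already refits every primary model without children who had prior artemisinin, applies Benjamini-Hochberg to that refit and reports it in Table 18. Without a pre-enrolment dose the two clocks coincide, so the refit removes the mismatch. The study calls itself hypothesis-generating. On-study exposure may be a fair proxy for exposure after an earlier dose in the same child, in which case deletion loses information: at λ = 0.8 it costs about 0.03, 0.07 and 0.13 of 24-hour power at *f* = 10%, 20% and 30%. Temperature and blood pressure are taken about every 6 hours, so with one prior dose mainly laboratory markers suffer. Section 6.5 limits each analysis to children measured at the timepoint of interest, and Table 13 lists baseline separately, so a baseline record was perhaps never meant to be a response.

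Much of this stands as a limit on size: the share is unknown, zero association is the worst case, and the proposed rule leaves some 24-hour responses inside the AUC window. It does not remove the fault. The refit is only a sensitivity analysis; it also drops correctly ordered pre-treated children and keeps baseline records used as responses in untreated ones. Prior therapy is only a candidate covariate and cannot restore time order. Section 6.5 adds no eligibility rule to Section 8.1, so whatever was intended, the rule as written admits the baseline record.

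**Conclusion.** The concern holds. By the SAP's own definitions, the primary 24-hour tests can include responses taken before the exposure (nominally always when the first on-study dose is the 24-hour dose) and laboratory responses that are the baseline record. Up to 44 of 176 tests are open to this, 28 of them on laboratory markers; a few 48-hour values may be too.

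The size depends on shares the documents do not give. At 5% or fewer misordered children, 24-hour power falls by at most 0.06 and average power stays at 0.87 to 0.88. At 20% with no association kept, it falls to 0.59, against 0.77 if the values are set to missing; the two approaches break even when about half the association is kept. These figures assume N = 80, independent tests and a true R² of 0.2. Interpretability is the main reason to act, and the plan should be corrected.

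**What to change.** Keep the first-dose clock and add to SAP Section 8.1:

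> A measurement is eligible as the 24-hour or 48-hour response only if it was collected after the first on-study dose of IV artesunate and is not the record used as baseline; otherwise the response at that timepoint is missing (Section 6.5).

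Report the number of values removed by timepoint and marker. As a sensitivity analysis, repeat the AUC0-12 tests requiring the response to follow the end of the 0–12 hour window. This should not be primary, because it removes every 24-hour response in children whose first on-study dose is the 12-hour dose.

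The cost is one sentence, one derivation rule and one set of counts, with no new data. Some 24-hour values and a few 48-hour values in pre-treated children become missing, as does the 24-hour laboratory value of any other child with no draw between the on-study dose and hour 24. Power is lost if misordered children keep more than about half the association. Excluding baseline records cost no power in the scenarios examined.
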